4.4.1 Dose Selection

The RP2D of Grapiprant is suggested as 300 mg BID (twice a day) from the ongoing phase I clinical trial for colorectal cancer (CRC) and non-small cell lung cancer (NSCLC). Those trials observed acceptable tolerability when it was combined with an immune-checkpoint inhibitor. The most frequent adverse event was liver toxicity (elevated GGP and ALP). Also, a G2/3 hepatic event was observed for 18.5% at 300 mg BID in the CRC study and 14.3% in the NSCLC study (See the investigator brochure). Base on the result from phase I trials, we will start the grapiprant from 300 mg in phase Ib If we observe dose-limiting toxicity (DLT) with 300 mg BID, the dosing will go down to 200 mg BID and re-evaluate the safety (see the section of **statistical analysis plan [7.0]**). One cycle is defined as 21 days. Grapiprant will be administered orally every day of each cycle. A research medication diary will be used for source documentation. Patients will follow dosing instructions as below:

- Patients will take grapiprant daily as instructed dependent on their assigned dose. Patients are encouraged to take study drug with food or within 2 hours after eating as food is known to decrease common mild gastrointestinal adverse events in drugs of a similar class (COX-2 inhibitors). Patients are to maintain a normal diet.
- Patients should take grapiprant every 12 hours at approximately the same time each day and evening, and not to take more or less than the prescribed dose at any time.
- Patients should swallow the tablets whole and not chew, crush, or break them with about 8 oz water.
- The date, amount taken, and time of study drug administration will be recorded daily in a research medication diary.
- If vomiting occurs, the patient should not take a replacement dose but should attempt to take their next scheduled dose if they are able. Any dose variations due to vomiting should be recorded on the research medication diary.

Product: Grapiprant
Protocol 2021-0077 Proprietary Information of MD Anderson

PI: [name] Co-PI: [name] Date: 11/22/2022

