4.4.2 Dose Modification

For patients who do not tolerate the protocol-specified dosing schedule, adjustments in grapiprant and eribulin doses are permitted to allow the patient to continue the study treatment. All dose modifications must be based on the worst preceding toxicity as graded by the NCI-CTCAE version 5.0. Those will also be counted as DLT when it meets DLT definition. The DLT will be defined as any of the following be "probable," "possible," and "definite events occurring in the first 21 days (cycle 1):

- Any Grade 3 hematologic toxicity with the following changes: grade 3 platelet count (< 50,000/mm³–25,000/mm³) with associated bleeding (without bleeding, grade 4 platelet count [< 25,000/mm³] will be defined as DLT); grade 3 absolute neutrophil count (<1,000–500/mm³) that persists for 7 or more days despite of the use of the grown factor support or that is associated with fevers (febrile neutropenia). (Otherwise, grade 4 absolute neutrophil count [< 500/mm³] will be defined as DLT.)
- Hepatocellular injury is indicated by 3-fold or greater elevations above the ULN of ALT or AST in addition to the elevation of serum total bilirubin > 2 x baseline. In such cases, no other reason can be found to explain the combination of increased transaminases and total bilirubin such as viral hepatitis, preexisting or acute liver disease, or another drug capable of causing the observed injury (Hy's Law). For patients with liver metastasis, 6-fold or greater elevations above the baseline of ALT or AST in addition to the elevation of serum total bilirubin > 4 x baseline.
- All other grade 3+ electrolyte abnormality associated with clinical symptoms, regardless of duration.
- Grade 3 nausea or vomiting that does not improve to Grade 1 within 72 hours of initiating supportive therapy.
- Any other non-hematologic grade ≥ 3 toxicity deemed to be related to the study drug that lasts 72 hours or more will be considered a DLT.
- A grade \geq 3 laboratory abnormality that is determined to be of no clinical significance by the investigators will not necessarily constitute a DLT.
- Any death not clearly due to the underlying disease or extraneous causes.

Dose modification at the time of toxicities will be conducted as follows:

Product: Grapiprant
Protocol 2021-0077 Proprietary Information of MD Anderson
[name]
Product: Grapiprant

PI: [name] Co-PI: [name] Date: 11/22/2022

Grapiprant

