Grade 1	Maintain dose level.
Grade 2	Omit dose until resolved to ≤ Grade 1, then restart at the same dose.
Grade > 3	Omit dose until resolved to ≤ Grade 1, then decrease 1 dose level.
HEPATIC	
AST or ALT	
Grade 1 (> ULN-3.0 x ULN)	Maintain dose level with liver function tests (LFTs)** monitored per protocol
Grade 2 (> 3.0– 5.0 x ULN) without	Omit dose until resolved to \(\le \text{Grade 1, then} \)
total bilirubin elevation to > 2.0 x ULN	-If resolved in ≤ 7 days, maintain dose level -If resolved in > 7 days, decrease 1 dose level
Grade 3 (> 5.0– 20.0 x ULN) without total bilirubin elevation to > 2.0 x ULN	Omit dose until resolved to ≤ Grade 1, then decrease 1 dose level
Grade 4 (> 20.0 x ULN) without bilirubin elevation to > 2.0 x ULN	Permanently discontinue patient from eribulin
AST and/or ALT and Albumin	

Product: Grapiprant

Protocol 2021-0077 Proprietary Information of MD Anderson

DI. [name]

PI: [name] Co-PI: [name] Date: 11/22/2022

AST and/or ALT > ULN-3.0 x ULN (grade 2) and albumin < LLN - 3 g/dL (grade 1)	Omit dose until resolved to ≤ Grade 1, then -If resolved in ≤ 7 days, maintain dose level -If resolved in > 7 days, decrease 1 dose level				
AST and/or ALT > 3.0–5.0 x ULN and albumin < 3 - 2 g/dL (grade 2) without total bilirubin elevation to > 2.0 x ULN	Permanently discontinue patient from eribulin				
Bilirubin (*for patients with Gilbert Syndrome these dose modifications apply to changes in direct bilirubin only)					
Grade 1 (> ULN-1.5 x ULN)	Maintain dose level with LFTs** monitored per protocol				
Grade 2 (> 1.5–3.0 x ULN) with ALT or AST \leq 3.0 x ULN	Omit dose until resolved to \leq Grade 1, then: If resolved in \leq 7 days, then maintain dose level If resolved in $>$ 7 days, then decrease 1 dose level				
Grade 3 (> 3.0– 10.0 x ULN) with	Permanently discontinue patient from eribulin				

Dose Modifications for eribulin

ALT or AST $\leq 3.0 \text{ x ULN}$

*Hepatic toxicity monitoring for patients with Gilbert Syndrome: total and direct bilirubin must be monitored, intensified monitoring applies to changes in direct bilirubin only; the monitoring includes the following LFTs: albumin, ALT, AST, total bilirubin, alkaline phosphatase.

LFTs include albumin, ALT, AST, total bilirubin, alkaline phosphatase, and GGT

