- Cycle 1 and 2: every other week (if visit schedule allows more frequent monitoring, this should be considered) or more frequently if clinically indicated, especially for patients with borderline acceptable AST/ ALT/ bilirubin* values
- Cycle 3 and onward: monthly or more frequently if clinically indicated

In case of any occurrence of ALT/AST/ bilirubin* increase \geq grade 2, LFTs must be monitored weekly or more frequently if clinically indicated until resolved to \leq grade 1.

In case of any occurrence of ALT/ AST/ bilirubin* increase \geq grade 3 LFTs must be monitored weekly or more frequently if clinically indicated until resolved to \leq grade 1; thereafter, the monitoring should be continued every other week or more frequently if clinically indicated. until the end of treatment with study medication

Patients who discontinued treatment with eribulin should be monitored weekly, including LFTs* or more frequently if clinically indicated until resolved to \leq grade 1 or stabilization (no CTCAE grade change over 4 weeks).

All other AEs	
Grade 1 or 2	Per physician discretion.
Grade 3	Omit dose until resolved to ≤ Grade 1, then decrease 1 dose level.
Grade 4	Permanently discontinue the patient from eribulin. Note: Omit dose for ≥ Grade 3 vomiting or Grade 3 nausea only if the vomiting or nausea cannot be controlled with optimal antiemetic treatment.

Protocol 2021-0077 Proprietary Information of MD Anderson PI: [name]

Co-PI: [name] Date: 11/22/2022

Dosing interruptions are permitted in the case of medical/surgical events or logistical reasons not related to study therapy (e.g., elective surgery, unrelated medical events, patient vacation, and/or holidays). Subjects should be placed back on study therapy within 3 weeks of the scheduled interruption. The reason for interruption should be documented in the patient's study record. Subjects who experience a recurrence of the same severe or life-threatening event at the same grade or greater with a re-challenge of grapiprant will be discontinued from trial treatment.

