		\A(I) 4	Cycle 2 and beyond				returns for follow up	30-days Safety F/U ^g	Follow-Up h	
Scheduling Window (Days):		Wk 1 ± 3	Wk 2	Wk 3 ± 3	Wk 4 ± 3	Wk 5 ± 3	# 3	± 7	30 days after the last dose	Yearly, up to 5 years after off study
Informed Consent	Х									
Inclusion/Exclusion Criteria	х									
Grapiprant Administration (daily)		Х	Х	Х	Х	Х	Х			
Eribulin Administration		Х	Х		Х	Х				
Physical Exam ^a , PS ^a	Х	Х			Х			Х		
V/S	Х	Х	Х		Х	Х		Х		
Adverse Events a	X	Х			Х			Х	Х	
Pregnancy Test – Urine or Serum β-HCG (for women with childbearing potential) ^j	Х									
Echo or MUGA ^d	Х									
EKG ^d	Х									
CBC (with diff) ^a	X	Х	Х		Х	Х		Х		
CRP b,	x				Х					
Biochemical Profiles, i, a	х	х			Х			x		
CT scan and bone scan, or PET-CT. Breast MRI, mammogram and/or ultrasound per SOC.	х							х		
Research tumor tissue Collection (metastatic site or primary site [if available]) ^e	Х				х					
Research Blood/Urine Collection f	Х				Х					
Survival Status ^h										Х

Product: Grapiprant Protocol 2021-0077 PI: [name] Co-PI: [name] Date: 11/22/2022

- a. Labs, PS and AEs will not be repeated if it was done within 8 (+/-3 days) days before starting treatment on Wk 1. PE at Wk 1 and day 1 of all subsequent cycles per physician discretion as clinically indicated
- b. C-reactive protein (CRP) will be obtained at baseline and at C2D1 (prior to treatment).
- c. As an evaluation of response, imaging analysis will be performed at baseline, after 2 cycles (C3) of proposed treatment (does not include window period), then at the end of every 3 cycles (C6, C9, C12, etc.). The other radiological evaluation may include ultrasound, bone scan, and X-rays, brain MRI, PET/CT, chest wall/breast photos as clinically indicated for a standard of care.
- d. ECHO, MUGA and EKG will be performed at baseline and as clinically indicated thereafter.
- e. Tumor tissue at the metastatic site or primary site (if available, exclude axillar lymph node) will be collected at baseline and C2D1 (prior to treatment). If the patient had both primary and distant metastasis sites, we would collect sample from the primary site only (excluding axillar lymph node). The biopsy will be done by core needle biopsy, but punch biopsy will be considered if the primary site was a superficial disease. CT-guided biopsy or ultrasonography-guided biopsy will be used based on the location of the metastasis site.

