- f. Peripheral blood and urine for correlative studies. Approximately 20 ml of blood (one 10 ml EDTA tube and one 10 ml Red top tube for the serum and PBMCs collection) will be drawn at baseline and after C2D1 (prior to treatment). For the urine sample, we will collect 10 ml of sample in the urinalysis tube. Urine creatinine will be performed centrally at LabCorp from the frozen urine samples which will be shipped to them in batches.
- g. The mandatory Safety Follow-Up should be conducted approximately 30 days after the last dose of the proposed treatment or before initiating a new anti-cancer treatment, whichever comes first. All AEs that occur before the safety follow-up visit should be recorded. Safety follow-up can be done in the clinic or by phone if the patient cannot come to the clinic for follow-up.
- h. The survival follow-up will be performed yearly for survival status, up to 5 years, if the patient is unable to come to the clinic, the follow-up will be done by chart review or by phone.
- i. Biochemical profiles/CMP (albumin, alkaline phosphatase, ALT, AST, LDH, GGT, uric acid, calcium, glucose, phosphorus, potassium, sodium, magnesium, total bilirubin, total protein, BUN, creatinine.
- j. Screening Pregnancy test should be done within 7 days before the start of an initial regimen to be consistent with institutional policy CLN1114.

Product: Grapiprant
Protocol 2021-0077
PI: [name]
Co-PI: [name]
Date: 11/22/2022

b. Phase II:

			Treatment Cycles (1 cycle = 21 days)				End of Treatment	Post-Treatment				
	Screening /Baseline		ndow riod		Cycle 1	Wk	Cycle	2 and b	eyond	If patient returns for follow up	30-day Safety F/U ⁹	Survival Follow-Up ^h
		Wk 1	Wk 2	Wk 3	Wk 4	5	Wk 6	Wk 7	Wk 8			
Scheduling Window (Days):	Within 28 days	± 3	± 3	± 3	± 3	± 3	± 3	± 3	± 3	± 7	30 days after the last dose	Yearly, up to 5 years after off study
Informed Consent	Х											
Inclusion/Exclusion Criteria	X											
Grapiprant Administration (daily)		х	Х	х	х	х	Х	х	Х			
Eribulin Administration				Х	Х		Х	Х				
Physical Exam ^a , PS ^a	Х	Х		Х			Х			Х		
V/S	Х			Х	Х		Х	Х		Х		
Adverse Events a	Х	Х		Х			Х			Х	Х	
Pregnancy Test – Urine or Serum β- HCG (for women with childbearing potential) ^j	х											
Echo or MUGA ^d	Х											
EKG ^d	Х											
CBC (with diff) ^a	Х	Х		Х	Х		Х	Х		Х		
CRP b,	Х			Х								
Biochemical Profiles i, a	Х	Х		Х			Х			Х		
CT scan and bone scan, or PET-CT. Breast MRI, mammogram and/or ultrasound per SOC ^c	х									х		

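### Section 4.4.2 sets liver tests every other week in cycles 1 and 2, but Tables 5a and 5b mark chemistry only on day 1 of each cycle, so a site working from the calendar has no nominal post-dose liver panel on the combination inside the 21-day DLT window

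*Combined protocol and SAP*

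**What the plan says.** **The text.** The notes to Table 3 (section 4.4.2) define the panel: "LFTs include albumin, ALT, AST, total bilirubin, alkaline phosphatase, and GGT". They then set the interval by cycle: "Cycle 1 and 2: every other week", with closer monitoring to be considered where visits allow it, and afterwards "Cycle 3 and onward: monthly or more frequently if clinically indicated".

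**The calendar.** Footnote i to Tables 5a and 5b (section 4.13) places ALT, AST, total bilirubin and GGT in the chemistry row.
- In Table 5a (phase Ib) the row "Biochemical Profiles" is marked at screening, Wk 1 (C1D1), Wk 4 (C2D1) and end of treatment.
- In Table 5b (phase II) the row "Biochemical Profiles i, a" is marked at screening, window Wk 1, Wk 3 (C1D1), Wk 6 (C2D1) and end of treatment.
- Footnote a lets the Wk 1 labs (Table 5a) or the C1D1 labs (Table 5b) be skipped if they were done within 8 (± 3) days beforehand.
- No footnote to the row mentions the every-other-week interval.

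**The DLT.** Section 4.4.2 limits DLTs to "events occurring in the first 21 days (cycle 1"). The hepatic criterion is "3-fold or greater elevations above the ULN of ALT or AST" together with total bilirubin above twice baseline. Patients with liver metastasis have higher thresholds, set against baseline. DLT is a primary outcome (section 4.1). Two DLTs among three or six patients move grapiprant from 300 to 200 mg BID, and the same toxicities are watched during the first cycle in phase II (section 7.0).

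**The concern.** Two schedules for the same tests disagree, and they do so in the cycle on which the dose decision rests. The hepatic criterion consists of laboratory values, and early enzyme rises may be silent, so it may not be met unless someone draws blood. Section 4.4.2 asks for weekly tests after a grade 2 or higher rise, but that rule starts only once a rise has been found. It cannot make up for a panel that was never scheduled.

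The liver is also where the earlier data give reason to look. Section 7.0 names liver-enzyme elevation as the most frequent adverse event with grapiprant. Section 4.4.1 reports that "a G2/3 hepatic event was observed for 18.5% at 300 mg BID in the CRC study and 14.3% in the NSCLC study", in combination with a checkpoint inhibitor. Section 6.2 reports grade 2 or higher ALT elevation in 18% of eribulin patients whose baseline ALT was grade 0 or 1. At stake is whether every patient counted in the DLT decision had a scheduled opportunity to show this toxicity in the period that counts.

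**Working it through.** The plan gives no figure to reproduce here. The check is a count of days.

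**Inputs.** Cycle length 21 days, so C2D1 is nominally D22 and C3D1 is D43. DLT window D1 to D21. Visit allowance for C2D1 ± 3 days. Text interval 14 days in cycles 1 and 2.

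**Text schedule.** Draws at 1 + 14k: D1, D15, D29, D43. One post-dose draw, D15, lies inside D1 to D21. With ± 3 days it falls on D12 to D18, and all 7 dates are inside.

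**Calendar schedule.** Draws at 1 + 21k: D1, D22, D43. No post-dose draw is nominally inside D1 to D21. The interval is 21 days, or 25 − 1 = 24 days if C2D1 falls at +3, against 14 in the text. C2D1 may fall on D19 to D25, which is 7 dates; D19, D20 and D21 are inside, so 3 of 7.

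**What the day-1 draw adds.** In phase Ib it is taken before any study drug and footnote a can waive it, so D1 to D21 may hold no scheduled liver panel at all. In phase II the C1D1 panel, unless waived, follows 14 ± 2 days of grapiprant alone (section 4.3). It shows the liver on grapiprant but not on the combination.

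**From cycle 3.** The text asks for monthly tests and the calendar gives one every 21 days, so the text is met. The conflict is confined to cycles 1 and 2.

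**Are the blank cells intended?** The CBC row in the same tables is marked at day 8 as well as day 1. The calendar therefore does separate the two visits, and chemistry is left off day 8.

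**Schedules that would satisfy the text.**

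| Added marks | Draw days | Gaps (days) | Post-dose draw inside D1–21 |
|---|---|---|---|
| C1D15 and C2D8 | 1, 15, 22, 29, 43 | 14, 7, 7, 14 | D15 |
| C1D8 and C2D8 | 1, 8, 22, 29, 43 | 7, 14, 7, 14 | D8 |

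Both keep every nominal gap at 14 days or less. If the day-8 visit is delayed by the permitted week, the draw moves to 8 + 7 = D15, still inside the window.

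**The case against.** The strongest reply is that the protocol already requires the missing draw. A blank calendar cell does not cancel an instruction in the text, and a site following section 4.4.2 tests at about day 15. The calendar is not exhaustive either: on-treatment scans appear only in footnote c. This stands as far as it goes, but chemistry has no equivalent footnote, and a site that schedules from the calendar will not be sent back to the Table 3 notes. That Table 3 is headed as recommendations does not settle the matter, because the interval is set by cycle for all patients and everyone starts eribulin.

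A second reply is that a D22 reading is not a lost event. A DLT must occur, not be measured, within 21 days; a pre-dose C2D1 abnormality reflects cycle-1 exposure; and the phase Ib review follows completion of cycle 1, with IND Office approval needed before any expansion or dose change (section 7.0). This also stands, except that the plan does not say such a reading counts.

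Two stronger readings are tempting. A reader might infer that hepatic DLTs will be missed and an unsafe dose carried forward. The documents do not support that. The percentages quoted above are neither cycle-1 rates nor DLT rates, section 7.0 reports no DLT at 300 mg BID in the earlier trials, and section 6.2 mentions a single eribulin patient without documented liver metastases who had concurrent grade 2 ALT and bilirubin rises, which resolved. The 3 of 7 counts permitted dates; it is not a probability of missing an event.

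A reader might also infer that the CBC schedule needs an extra cycle-1 draw. No text in the plan contradicts that schedule, and an added draw could do harm. Grade 4 neutropenia was 29% on eribulin alone (section 6.2). If, as an upper bound, all of it fell in cycle 1 and was captured, P(at most 1 of 6) = 0.71⁶ + 6 × 0.29 × 0.71⁵ = 0.128 + 0.314 = 0.44. Eribulin alone would then trigger grapiprant de-escalation about 56% of the time.

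**Conclusion.** The conflict is real and limited to cycles 1 and 2: 14 days in the text against 21 in the calendar (24 at the edge of the visit allowance). On the calendar alone, no post-dose liver panel on the combination is nominally scheduled inside D1 to D21, and it falls there only if C2D1 is drawn early, on D19 to D21. The plan is silent on how to classify an abnormality first seen on D22 to D25. This should be corrected because it bears on a laboratory-defined part of a primary outcome that drives the dose decision.

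The conclusion depends on a site working from the calendar rather than the text; a site following section 4.4.2 has no gap. The effect on the number of DLTs, and so on the chance of keeping 300 mg BID, cannot be computed, because no cycle-1 hepatic DLT rate is given.

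**What to change.** Make the calendar match the text. Add chemistry marks to Tables 5a and 5b so that no nominal interval in cycles 1 and 2 exceeds 14 days and at least one post-dose panel falls inside D1 to D21. Either option does this:

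- **C1D15 and C2D8** (Wk 3 and Wk 5 in Table 5a; Wk 5 and Wk 7 in Table 5b). This sees later toxicity, but D15 needs a clinic or home-physician draw. Section 4.12, item 5 covers routine laboratory work by the home physician; section 4.11 is meant for unexpected incidents.
- **C1D8 and C2D8** (Wk 2 and Wk 5 in Table 5a; Wk 4 and Wk 7 in Table 5b). These are existing eribulin and CBC visits, so no visit is added, but liver injury arising after day 8 is not seen until C2D1.

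The C2D8 columns also stand for later cycles, so add a footnote limiting that chemistry mark to cycle 2. In the DLT definition, state that a laboratory abnormality in the pre-dose C2D1 panel counts toward the cycle-1 DLT assessment.

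The cost is one extra chemistry panel per cycle in cycles 1 and 2, already called for by section 4.4.2, plus the D15 draw under the first option. Nothing changes from cycle 3, and the CBC schedule stays as it is.

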4.5 Concomitant Medications/Vaccinations (allowed & prohibited)

Medications or vaccinations prohibited explicitly in the exclusion criteria are not allowed during the ongoing trial. If there is a clinical indication for one of these or other medications or vaccinations prohibited explicitly during the trial, discontinuation from trial therapy or vaccination may be required. The final decision on any supportive therapy or vaccination rests with the investigator and/or the subject's primary physician and will be documented in the subject's chart..

Acceptable Concomitant Medications

All treatments that the investigator considers necessary for a subject's welfare may be administered at the investigator's discretion in keeping with the community standards of medical care. Concomitant medication will be recorded as the standard of care in the subject's medical record.

Prohibited Concomitant Medications

Subjects are prohibited from receiving the following therapies during the study.

- NSAIDs, COX-2 inhibitors.
- Any anti-cancer agents.
- Radiation therapy.
 - Note: Radiation therapy to the symptomatic solitary lesion will be allowed. The treatment will be continued during the treatment.
- Live vaccines within 30 days before the first dose of trial treatment and while participating in the trial. Examples of live vaccines include, but are not limited to, the following: measles, mumps, rubella, chickenpox, yellow fever, rabies, BCG, and typhoid (oral) vaccine. Seasonal influenza vaccines for injection are generally killed virus vaccines and are allowed; however, intranasal influenza vaccines (e.g., Flu-Mist®) are live attenuated vaccines and are not allowed. Any mRNA vaccines for COVID-19 approved under an Emergency Use Authorization will be allowed in any case.
- Subjects who, in the assessment by the investigator, require the use of any of the treatments mentioned above for clinical management should be removed from the trial. Subjects may receive other medications that the investigator deems to be medically necessary. There are no prohibited therapies during the post-treatment follow-up phase.

Investigators should refer to the PI and associated addenda for complete details on the drug interaction potential of grapiprant. Highlights of drug interaction are summarized below.

 Grapiprant is a p-glycoprotein substrate, however, it is unknown if Grapiprant is a substrate of CYP450 enzymes. Use of strong inhibitors and inducers of CYP3A4 and p-glycoprotein have been restricted in prior studies with Grapiprant. In this study, participants taking strong CYP3A4 or P-

Protocol 2021-0077 Proprietary Information of MD Anderson PI: [name]

Co-PI: [name] Date: 11/22/2022

glycoprotein inhibitors or inducers are excluded from the study unless they can be transferred to other medications within ≥ 5 half-lives prior to dosing.

- Concomitant use of drugs that are strong CYP3A inhibitors should be avoided (eg, aprepitant, clarithromycin, itraconazole, ketoconazole, nefazodone, posaconazole, telithromycin, verapamil, and voriconazole).
- Concomitant use of drugs that are strong CYP3A inducers should be avoided (eg, phenytoin, rifampin, carbamazepine, St John's Wort, bosentan, modafinil, and nafcillin).
- Grapiprant is not an inhibitor of CYP450 enzymes, but it is unknown if Grapiprant is an inducer of CYP450 enzymes. The exposure of drugs that are CYP450 substrates may be reduced by concomitant use of Grapiprant.
- Concomitant use of drugs that are sensitive CYP450 substrates with a narrow therapeutic index should be avoided (e.g., warfarin, phenytoin, fentanyl).
- Strong CYP2C8 inhibitors (eg., gemfibrozil) should be used with caution with grapiprant.

Table 4: Examples of Narrow Therapeutic Index CYP450 Substrates

Narrow Therapeutic CYP substrate	Examples
CYP3A substrates	alfentanil, cyclosporine, ergotamine, fentanyl, pimozide, quinidine, sirolimus, tacrolimus,
CYP1A2 substrates	theophylline, tizanidine
CYP2C9 substrates	warfarin, phenytoin
CYP2C19	s-mephenytoin
CYP2D6 substrates	thioridazine

